10.3 RECORDING AEs AND SAEs

When an AE/SAE occurs, it is the responsibility of the Investigator to review all documentation (e.g. hospital notes, laboratory and diagnostic reports) related to the event. The Investigator will then record all relevant information in the CRF and on the SAE form (if the AE meets the criteria of serious).

Information to be collected includes dose, type of event, onset date, Investigator assessment of severity and causality, date of resolution as well as treatment required, investigations needed and outcome.

10.4 ASSESSMENT OF AEs AND SAEs

Seriousness, causality, severity and expectedness will be assessed by the Principal Investigator. For randomised double blind studies, AEs will be assessed as though the participant is taking active IMP. Cases that are considered serious, possibly, probably or definitely related to IMP and unexpected (i.e. SUSARs) will be unblinded.

The Investigator is responsible for assessing each AE.

The Chief Investigator (CI) may not downgrade an event that has been assessed by an Investigator as an SAE or SUSAR, but can upgrade an AE to an SAE, SAR or SUSAR if appropriate.

10.4.1 Assessment of Seriousness

The Investigator will make an assessment of seriousness as defined in Section 10.1.

10.4.2 Assessment of Causality

The Investigator will make an assessment of whether the AE/SAE is likely to be related to the IMP according to the definitions below.

- Unrelated: where an event is not considered to be related to the IMP.
- Possibly Related: The nature of the event, the underlying medical condition, concomitant medication or temporal relationship make it possible that the AE has a causal relationship to the study drug. The assessment of causality will be made against the reference safety information found in the Summary of Product Characteristics.

Where non Investigational Medicinal Products (NIMPs) e.g. rescue/escape drugs are given: if the AE is considered to be related to an interaction between the IMP and the NIMP, or where the AE might be linked to either the IMP or the NIMP but cannot be clearly attributed to either one of these, the event will be considered as an AR. Alternative causes such as natural history of the underlying disease, other risk factors and the temporal relationship of the event to the treatment should be considered and investigated. The blind should not be broken for the purpose of making this assessment.

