10.1 DEFINITIONS

An **adverse event** (AE) is any untoward medical occurrence in a clinical trial participant which does not necessarily have a causal relationship with an investigational medicinal product (IMP).

An **adverse reaction** (AR) is any untoward and unintended response to an IMP which is related to any dose administered to that participant.

A **serious adverse event** (SAE), **serious adverse reaction** (SAR). Any AE or AR that at any dose:

- results in death of the clinical trial participant;
- is life threatening*;
- requires in-patient hospitalisation[^] or prolongation of existing hospitalisation;
- results in persistent or significant disability or incapacity;
- consists of a congenital anomaly or birth defect;
- results in any other significant medical event not meeting the criteria above.

*Life-threatening in the definition of an SAE or SAR refers to an event where the participant was at risk of death at the time of the event. It does not refer to an event which hypothetically might have caused death if it were more severe.

[^]Any hospitalisation that was planned prior to randomisation will not meet SAE criteria. Any hospitalisation that is planned post randomisation will meet the SAE criteria.

A suspected unexpected serious adverse reaction (SUSAR) is any AR that is classified as serious and is suspected to be caused by the IMP, that it is not consistent with the information about the IMP in the Summary of Product Characteristics (SmPC) or Investigators Brochure.

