10.4.3 Assessment of Expectedness

If an event is judged to be an AR, the evaluation of expectedness will be made based on knowledge of the reaction and the relevant product information documented in the SmPC/IB.

The event may be classed as either:

Expected: the AR is consistent with the toxicity of the IMP listed in the SmPC/IB.

Unexpected: the AR is not consistent with the toxicity in the SmPC/IB.

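### Section 10.4.2 refers causality to the SmPC, the reference for expectedness; read literally, a serious unlisted reaction could be judged unrelated and miss SUSAR assessment

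*Protocol*

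**What the plan says.** Four parts of the Protocol bear on this point.

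- **Section 10.1** defines a SUSAR as a serious adverse reaction that "is suspected to be caused by the IMP, that it is not consistent with the information about the IMP" in the SmPC or Investigator's Brochure.
- **Section 10.4** sets the consequence: "Cases that are considered serious, possibly, probably or definitely related to IMP and unexpected (i.e. SUSARs) will be unblinded".
- **Section 10.4.2** offers two causality grades. The first reads "Unrelated: where an event is not considered to be related to the IMP". The second, possibly related, applies where the kind of event, the patient's underlying condition, "concomitant medication or temporal relationship make it possible that the AE has a causal relationship to the study drug". The same bullet then ends: "The assessment of causality will be made against the reference safety information found in the Summary of Product Characteristics". The paragraph that follows, on non-investigational products, asks for other explanations to be weighed: "Alternative causes such as natural history of the underlying disease, other risk factors and the temporal relationship of the event to the treatment".
- **Section 10.4.3** opens the next step only to some events: "If an event is judged to be an AR, the evaluation of expectedness will be made based on knowledge of the reaction" and the product information. Its second class is "Unexpected: the AR is not consistent with the toxicity in the SmPC/IB".

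No other part of the Protocol or SAP qualifies the sentence that refers causality to the SmPC.

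**The concern.** Causality and expectedness are separate questions. Causality asks whether the drug may have produced the event in this patient. Expectedness asks whether the reaction is already described for the product. A SUSAR needs yes to the first and no to the second. If the product information is consulted for both, it can count against an unlisted event at the first question, and the second is then never put.

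The investigator's grade matters because unblinding (10.4), the 7- and 15-day reports to the regulator and ethics committee (10.6), and inclusion in the annual list of SARs and SUSARs (10.6) all depend on it. Participants take study drug for 12 months (6.3) in a condition for which section 14.6 says ticagrelor is not licensed. Reactions not yet described are what the SUSAR process exists to find. Section 12.3 states that there will be no independent data monitoring committee, so the judgement made on each case carries more of the load.

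**Working it through.** No arithmetic applies: section 10.4 states no figure and the point depends on none. The check is to set the steps side by side and follow one kind of event through them.

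| Step | Section | Test applied | Reference |
|---|---|---|---|
| 1. Is it related? | 10.4.2, definition | Kind of event, underlying condition, other drugs, timing | Clinical judgement |
| 1. Is it related? | 10.4.2, last sentence of the same bullet | Comparison with reference safety information | SmPC |
| 2. Is it unexpected? | 10.4.3, only if step 1 gives an adverse reaction | Consistency with described toxicity | SmPC/IB |
| 3. Is it a SUSAR? | 10.1, 10.4 | Serious, related and unexpected | Results of steps 1 and 2 |

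Take a serious event that is not in the SmPC, begins soon after study drug is started, and has no other evident cause.

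1. **The clinical definition governs step 1.** Kind and timing make a causal link possible, so the event is possibly related and counts as an adverse reaction. Step 2 finds it unexpected. It is a SUSAR, is unblinded, and is reported within 7 or 15 days.
2. **The SmPC sentence governs step 1.** The reference offers no support for a link. The event may be graded unrelated, is then not an adverse reaction, and step 2 does not open. There is no SUSAR.
3. **Graded unrelated, then looked at again.** The SAE is still reported, and the Chief Investigator may upgrade it (10.4). It can become a SUSAR, but only if someone chooses to act.

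The text permits all three paths and gives no rule on which test in step 1 prevails. For an event that is in the SmPC, the choice does not affect SUSAR status: if judged related it is expected, so it is not a SUSAR under either test. The conflict therefore bites only on unlisted events.

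Next, whether another provision closes the gap:

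- **Assessment as if on active drug (10.4)** deals with blinding, not with listing.
- **Reporting to the sponsor's office within 24 hours (10.5)** covers every SAE, but the causality on the form is made under 10.4.2. Sections 10.5 and 10.6 describe no step in which that office reassesses it.
- **Reporting to the drug supplier within 7 days (10.7)** covers every SAE regardless of causality, but does not make an event a SUSAR.
- **Review of SAEs by the steering committee (12.2)** gives a second look, but no reassessment of causality is described.
- **The route for non-investigational products (10.4.2)** classes an event that might be due to either product as an adverse reaction without reference to the SmPC. The products named in 6.7.1 are tied to the scans, so for those products the route is narrow.

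One further comparison concerns the grades. Section 10.4 names possible, probable and definite relation, while 10.4.2 defines only possible. Since possible already suffices for a SUSAR, no case is lost by this.

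**The case against.** The strongest reply is that the sentence is loose but harmless. It does not say that an event must be listed to be related, and the unrelated grade is not defined as unlisted. The clinical grounds in the same bullet are alternatives, and none depends on the SmPC. Reading the sentence as the sole test would leave the unexpected class in 10.4.3, the unblinding of SUSARs and the expedited reports with almost nothing to act on, so a reading that gives them effect is more natural. Events graded unrelated are still seen by the sponsor's office, the drug supplier and the steering committee.

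Much of this stands, and it rules out three stronger readings that a reader might infer.

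- **That related events must all be listed, so no SUSAR can ever arise.** The clinical definition, the route for non-investigational products and the power to upgrade each allow one. In addition, 10.4.3 asks about consistency with described toxicity and draws on the IB and on knowledge of the reaction, which is not simply the SmPC list in reverse.
- **That investigators will tend to grade unlisted events as unrelated.** This predicts behaviour that the documents neither describe nor allow to be measured.
- **That causality decides what enters the SAP's safety tables.** SAP section 7.6 summarises adverse events by causality among other features and lists each one. An event graded unrelated would still appear, though perhaps under the wrong label.

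What does not stand is that the safeguards settle the matter. The upgrade is discretionary, and general SAE reporting triggers neither unblinding nor the 7- or 15-day clock. The sentence is also worded as a requirement, so an investigator who applies it as the test is following the Protocol.

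**Conclusion.** The point holds as an internal inconsistency with a possible safety-reporting consequence. Section 10.4.2 gives two tests for causality that can disagree for serious events absent from the SmPC, and nothing says which prevails. Under one of them such an event could be judged unrelated and miss SUSAR assessment, unblinding and expedited reporting.

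Only the direction can be stated, not the size. The documents give no expected number of unlisted serious events and nothing on how the sentence would be applied. The conclusion rests on the sentence being open to a literal reading and on there being no routine second assessment of causality outside these documents; if the sponsor's procedures include one, the risk is smaller. The mismatch in causality grades between 10.4 and 10.4.2 is editorial.

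**What to change.** Delete the sentence in 10.4.2 that refers causality to the SmPC. Alternatively, keep the bullet and add that whether an event is listed has no bearing on whether it is judged related. Causality then rests on the nature of the event, its timing, the underlying disease, other medication and alternative causes. Since the request to consider alternative causes now sits in the paragraph on non-investigational products, make clear that it applies to every event. Use the SmPC/IB in 10.4.3 only, for expectedness.

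As an editorial change, use one set of causality grades in 10.4 and 10.4.2.

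The cost is a short amendment under section 14.1 and matching guidance for the SAE form. The downside is small: a few more events may be graded possibly related and assessed for expectedness, and any that prove to be SUSARs would be unblinded, as 10.4 already intends. No sample size, endpoint or planned analysis changes.

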10.4.3 Assessment of Expectedness

If an event is judged to be an AR, the evaluation of expectedness will be made based on knowledge of the reaction and the relevant product information documented in the SmPC/IB.

The event may be classed as either:

Expected: the AR is consistent with the toxicity of the IMP listed in the SmPC/IB.

Unexpected: the AR is not consistent with the toxicity in the SmPC/IB.

10.4.4 Assessment of Severity

The Investigator will make an assessment of severity for each AE/SAE and record this on the CRF or SAE form according to one of the following categories:

Mild: an event that is easily tolerated by the participant, causing minimal discomfort and not interfering with every day activities.

Moderate: an event that is sufficiently discomforting to interfere with normal everyday activities.

Severe: an event that prevents normal everyday activities.

Note: the term 'severe', used to describe the intensity, should not be confused with 'serious' which is a regulatory definition based on participant/event outcome or action criteria. For example, a headache may be severe but not serious, while a minor stroke is serious but may not be severe.

10.5 REPORTING OF SAEs/SARs/SUSARs

Once the Investigator becomes aware that an SAE has occurred in a study participant, the information will be reported to the ACCORD Research Governance & QA Office **immediately or within 24 hours**. If the Investigator does not have all information regarding an SAE, they should not wait for this additional information before notifying ACCORD. The SAE report form can be updated when the additional information is received.

The SAE report will provide an assessment of causality and expectedness at the time of the initial report to ACCORD according to Sections 10.4.2, Assessment of Causality and 10.4.3, Assessment of Expectedness.

The SAE form will be transmitted by fax to ACCORD on **[name]** or may be transmitted by hand to the office or submitted via email to [contact]. Only forms in a pdf format will be accepted by ACCORD via email.

Where missing information has not been sent to ACCORD after an initial report, ACCORD will contact the investigator and request the missing information.

All reports faxed to ACCORD and any follow up information will be retained by the Investigator in the Investigator Site File (ISF).

10.6 REGULATORY REPORTING REQUIREMENTS

The ACCORD Research Governance & QA Office is responsible for pharmacovigilance reporting on behalf of the co-sponsors (Edinburgh University and NHS Lothian).

The ACCORD Research Governance & QA Office has a legal responsibility to notify the regulatory competent authority and relevant ethics committee (Research Ethics Committee (REC) that approved the trial). Fatal or life threatening SUSARs will be reported no later than 7 calendar days and all other SUSARs will be reported no later than 15 calendar days after ACCORD is first aware of the reaction.

ACCORD will inform Investigators at participating sites of all SUSARs and any other arising safety information.

An Annual Safety Report/Development Safety Update Report will be submitted, by ACCORD, to the regulatory authorities and RECs listing all SARs and SUSARs.

10.7 ASTRA ZENECA REPORTING REQUIREMENTS

All SAEs will be reported to AstraZeneca within 7 days, whether or not considered causally related to the investigational product.

The report will indicate, either in the SAE report or the cover page, the causality of events in relation to all study medications and if the SAE is related to disease progression, as determined by the principal investigator.

A cover page/the SAE report will detail the following:

- Investigator Sponsored Study (ISS)
- The Investigator IND number assigned by the FDA
- The Investigator's name and address
- The trial name/title and AstraZeneca ISS reference number

The SAE report will be sent [with the accompanying cover page] by fax to AstraZeneca's designated fax line: [name] or by email to:

[contact]

10.8 FOLLOW UP PROCEDURES

After recording and reporting an SAE, the Investigator will follow each participant until resolution or death of the participant. Follow up information on an SAE will be reported to the ACCORD office.

After initially recording an AE, the Investigator should follow each AE until resolution of the event or until no longer medically indicated.

11 PREGNANCY

Woman of child-bearing potential will not be enrolled into the trial (woman who have experienced menarche, are pre-menopausal, have not been sterilised or who are currently pregnant).

Pregnancy is not considered an AE or SAE; however, the Investigator will collect pregnancy information for any female participants or female partners of male participants who become pregnant while participating in the study. The Investigator will record the information on a Pregnancy Notification Form and submit this to the ACCORD office within 14 days of being made aware of the pregnancy.

All pregnant female participants and partners of male participants will be followed up until following the outcome of the pregnancy.

All outcomes of pregnancy will be reported to AstraZeneca.

12 TRIAL MANAGEMENT AND OVERSIGHT ARRANGEMENTS

12.1 TRIAL MANAGEMENT GROUP

The trial will be coordinated by a Project Management Group, consisting of the grant holders (Chief Investigator and Principal Investigator in Edinburgh) and a coordinating Clinical Research Facility nurse.

The Principal Investigator will oversee the study and will be accountable to the Chief Investigator. The Principal Investigator will be responsible for checking the CRFs for completeness, plausibility and consistency. Any queries will be resolved by the Investigator or delegated member of the trial team.

A Delegation Log will be prepared for each site, detailing the responsibilities of each member of staff working on the trial.

12.2 TRIAL STEERING COMMITTEE

A Trial Steering Committee (TSC) will be established to oversee the conduct and progress of the trial. The review of SAEs will be added to the TSC agenda to ensure that appropriate action is taken if any safety issues arise.

12.3 DATA MONITORING COMMITTEE

In the PLATElet inhibition and patient Outcomes (PLATO) trial of 18,624 patients presenting with an acute coronary syndrome, ticagrelor was superior to clopidogrel for the prevention of cardiovascular events and death [Wallentin *et al*, 2009]. There were modest increases in the risks of bleeding and low rates of other side effects, such as dyspnoea. It is extremely unlikely that we will observe any substantial increased risk in our trial population given the small sample size of 250 patients and the very similar disease population in the PLATO trial that had a 100-fold larger trial population size. For this reason, an independent Data Monitoring Committee (DMC) will not be convened for this study and all study adverse events will be reported to the sponsors and AstraZeneca and will be discussed by the TSC.

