2.1.3 Safety Objective

To determine whether the addition of ticagrelor to standard optimal medical therapy is safe and well tolerated in patients with stable coronary heart disease on optimal medical therapy. All bleeding events will be categorised according to the previous PLATO criteria [Wallentin *et al*, 2009] and recorded on the CRF.

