4.3 Exclusion Criteria

Subjects should not enter the study if any of the following exclusion criteria are fulfilled:

1. An acute coronary syndrome within the last 12 months
2. An indication for dual anti-platelet therapy, such as drug eluting stent
3. Receiving thienopyridine therapy such as clopidogrel or prasugrel
4. Percutaneous coronary intervention or coronary artery bypass graft surgery within the last 3 months
5. Inability or unwilling to give informed consent
6. Women who are pregnant, breastfeeding or of child-bearing potential (women who have experienced menarche, are pre-menopausal and have not been sterilised) will not be enrolled into the trial
7. Known hypersensitivity to ticagrelor or one of its excipients
8. Active pathological bleeding or bleeding diathesis
9. Significant thrombocytopenia: platelets $<100 \times 10^9 /L$
10. History of intracranial haemorrhage
11. Moderate to severe liver impairment (Child's Grade B or C)
12. Maintenance therapy with strong CYP3A4 inhibitors, such as ketoconazole, nefazodone, ritonavir, indinavir, atazanavir, or clarithromycin
13. Major intercurrent illness or life expectancy <1 year
14. Renal dysfunction (eGFR $\leq 30 \text{ mL/min}/1.73 \text{ m}^2$)
15. Contraindication to iodinated contrast agents
16. Planned coronary revascularization or major non-cardiac surgery in the next 12 months
17. Maintenance therapy with simvastatin or lovastatin at doses greater than 40mg daily
18. Receiving oral anticoagulants including warfarin, rivaroxaban, dabigatran or apixaban.

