7.1 SAFETY ASSESSMENTS

The study does not have any pre-specified safety outcome measures. However, all bleeding events will be categorized according to the previous PLATO criteria [Wallentin *et al*, 2009]. These will be reported through adverse event reporting mechanisms (see Section 10).

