### **7.6 Safety analyses**

These analyses will use the safety population. Adverse Events (AEs) will be summarised by treatment received and by seriousness, causality, expectedness, and severity of event. If available, events will be reported by MedDRA preferred terms and grouped by System Organ Class. If a patient has multiple reports of the same event, only the event reported at the highest grade will be included. Each patient will be counted only once in a summary of events by System Organ Class. No formal statistical analysis will be

performed. A listing will be produced detailing each event, and what happened to the patient subsequently.

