#### **7.6.1 Bleeding**

These analyses will use the safety population. To determine whether the addition of ticagrelor to standard optimal medical therapy is safe and well tolerated in patients with stable coronary heart disease on optimal medical therapy.

All bleeding events will be summarised by treatment received and categorised according to the 2009 PLATO criteria [Wallentin et al, 2009]. No formal statistical analysis will be performed. Time to each bleeding event from study entry and description of the bleeding event will be provided.

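### The plan aims to determine whether ticagrelor is safe but names no safety outcome and plans no between-arm estimate; the stated reasons for having no DMC also contain errors

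*Protocol*

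**What the plan says.** Protocol 2.1.3 gives the safety objective as "To determine whether the addition of ticagrelor to standard optimal medical therapy is safe and well tolerated" in stable patients on optimal therapy, and SAP 7.6.1 restates it above the bleeding analysis.

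Protocol 7.1 then says: "The study does not have any pre-specified safety outcome measures". Its next sentence adds that "all bleeding events will be categorized according to the previous PLATO criteria", with reporting through the adverse event system.

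SAP 7.6 tabulates adverse events by treatment received, seriousness, causality, expectedness and severity, with a listing. SAP 7.6.1 says: "All bleeding events will be summarised by treatment received and categorised according to the 2009 PLATO criteria". It adds the time to, and a description of, each bleed. It also says: "No formal statistical analysis will be performed". SAP 7.6 says the same of adverse events in general.

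Protocol 12.3 explains why no independent Data Monitoring Committee is convened. It cites an earlier trial of 18,624 acute coronary syndrome patients comparing ticagrelor with clopidogrel. It argues that a substantial excess risk is very unlikely to be seen here, given "the small sample size of 250 patients and the very similar disease population in the PLATO trial that had a 100-fold larger" trial population. In the same place it routes all adverse events to the sponsors, the manufacturer and the TSC, and Protocol 12.2 puts serious adverse events on the TSC agenda.

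**The concern.** There are two linked problems.

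First, the objective asks a question that no planned output answers. Determining whether adding a drug is safe needs at least a named outcome, an estimate of the excess over control, and a measure of its uncertainty. The plan has none of these for safety. The general promise of 95% intervals in SAP 6 does not help, because no safety estimate is defined for an interval to accompany. SAP 7.6.1 summarises bleeding events rather than patients, so even the number of patients with at least one bleed in each arm is not assured.

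Second, the reasons recorded for having no DMC do not match the rest of the protocol. The sample size differs, the population is called similar although the eligibility criteria make it different, and a bleeding excess over another platelet inhibitor stands in for the excess over placebo. A small sample is also a reason why harm may go unseen; it is not evidence that the risk is low.

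At stake are how a short bleeding table may be read and the accuracy of a recorded oversight decision. The primary troponin analysis is unaffected.

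**Working it through.** **Sample size.** Protocol 4.1, Protocol 9.1 and SAP 3 all give 220. Protocol 9.1 builds up to it: 55 per group × 2 / 0.60 = 183.3, so 183 patients with 30-day data, raised to 220 for early withdrawal. The 183 reproduces. The 250 in Protocol 12.3 is the outlier.

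**Size multiple.** 18,624/250 = 74.5; 18,624/220 = 84.7; 18,624/183 = 101.8. A 100-fold ratio fits neither total. It fits only the number needed with 30-day data, which is not the number in that sentence.

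**Population and comparator.**

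| | Cited trial (Protocol 1.1.2, 12.3) | This trial |
|---|---|---|
| Population | Acute coronary syndrome | Stable disease; excludes "An acute coronary syndrome within the last 12 months" (4.3) |
| Control | Clopidogrel | Placebo (3.1), with aspirin in all patients (6.7.2); thienopyridine users excluded (4.3) |

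An excess of bleeding measured over clopidogrel does not bound the excess over placebo.

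**What the safety data could show.** Assume 220 patients split 1:1, so n = 110 per arm. The documents give no placebo event rates, so every scenario below is hypothetical.

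- *No major bleeds on ticagrelor.* The exact two-sided 95% upper limit is 1 − 0.025^(1/n) = 1 − 0.025^(1/110) = 3.3%. With 92 per arm (about half of 183) it is 3.9%.
- *3 versus 1 patients with an event.* The proportions are 2.73% (Wilson limits 0.93 to 7.71) and 0.91% (0.16 to 4.97), a difference of 1.82 points. Newcombe limits: lower = 1.82 − √((2.73 − 0.93)² + (4.97 − 0.91)²) = −2.6; upper = 1.82 + √((7.71 − 2.73)² + (0.91 − 0.16)²) = +6.9.
- *Dyspnoea.* Protocol 12.6.2 quotes 14% on ticagrelor in the cited trial. The 95% half-width is 1.96 × √(p₁(1 − p₁)/110 + p₂(1 − p₂)/110). With p₁ = 14% and placebo assumed at 3%, 7% or 14%, it is 7.2, 8.0 or 9.2 points.
- *Rarer events.* By the same formula, an assumed 5% versus 2% gives 4.8 points and 3% versus 1% gives 3.7 points. Each half-width exceeds the difference itself (3 and 2 points).

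A table with few bleeds in either arm could therefore sit alongside a true excess of several percentage points, and no planned output would show this.

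**The case against.** The strongest reply is that this is a small mechanistic trial. Protocol 5.5 says as much, and descriptive safety tables are usual in such a trial. Safety is not ignored: bleeds are classified, tabulated by treatment received and timed, and SAP 7.6 counts each patient once within a system organ class. Neither document says that a claim of safety will be made from a low count. All of this stands. It makes the gap one of a missing estimate rather than missing data, and the harm from misreading a possibility rather than a plan.

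On oversight, the TSC considers adverse events, the sponsors and manufacturer receive them, SUSARs are unblinded (Protocol 10.4) and annual safety reports go to the authorities (10.6). Protocol 4.3 also excludes patients with bleeding diathesis, low platelets, previous intracranial haemorrhage or oral anticoagulants, which bears on absolute bleeding risk. This stands too.

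A reader might infer that a DMC was required, or that bleeding goes unwatched. The documents support neither. They do not state the TSC's composition or whether it sees data by arm, so the most that can be said is that this is unspecified. Nor do they support requiring a declaration that no safety conclusion will be drawn, or a formal re-confirmation of the no-DMC decision. The size multiple may be loose rounding and changes nothing.

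What the reply does not answer is the wording of the objective, or the conflict between Protocol 12.3 and the protocol's own sample size, eligibility and control arm.

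**Conclusion.** The concern holds in a limited form. The stated aim of determining safety has no named outcome and no between-arm estimate behind it. At about 110 per arm, counts alone cannot meet it: zero events leaves risks up to 3.3% open, and an illustrative 3 versus 1 spans −2.6 to +6.9 points. These figures assume 220 patients, a 1:1 split and hypothetical event counts.

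The reasons in Protocol 12.3 are wrong as written on sample size (250 against 220) and on similarity of population, and they rely on a bleeding comparison with the wrong control for this trial. That faults the reasoning, not necessarily the decision: having no DMC may be defensible on accurate grounds. The change is worth making and cheap, and it does not touch the primary analysis.

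**What to change.** 1. In SAP 7.6.1, for PLATO major, major-or-minor and any bleeding, and for dyspnoea, report the number of patients with at least one event by arm in the safety population, and the risk difference with a 95% CI. Use a method suited to small counts, such as Newcombe's. No significance test is needed.
2. In Protocol 2.1.3 and SAP 7.6.1, reword the objective so that the trial estimates (or describes) the excess of bleeding and other adverse events over placebo.
3. In Protocol 12.3, change 250 to 220, remove the claim that the populations are very similar, and state that the cited bleeding excess was measured against clopidogrel in acute coronary syndrome. Rest the no-DMC decision on reasons that hold, including the TSC review of adverse events already planned. The size multiple can be corrected or dropped in the same edit.

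The cost is some wording and a few table columns. The downside is that wide intervals will be visible and the safety statement will read as weaker, which reflects what the design can support.
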